### **7.2.4 Secondary and Exploratory Outcomes**

General considerations: The secondary and exploratory endpoints require a variety of standard analytical methods along with sophisticated analytical strategies.

For the secondary endpoint of HF-related readmission, the same analytical approach described for the primary outcome measure will be used. The time to (first) hospital readmission will be modeled using a Kaplan-Meier survival and tested using a stratified log-rank test.

[figure not shown]
For all-cause mortality, the difference in the hazard for death will be tested using a stratified log-rank test on the intention-to-treat sample.

For the exploratory outcomes involving serial measurements originating from the device, longitudinal summary statistics will also be used to condense the longitudinal data stream into meaningful summary measures (e.g., daily mean BP, incremental AUCs) prior to analysis. Longitudinal changes in weight and other continuous measures such as HR and

blood pressures will be modeled using mixed effects models that incorporate random slope and intercept effects.

When the patient is actively monitoring with a BodyGuardian® Control Unit, an activity measure is gathered every 60 seconds. This measure is gathered regardless of the signal quality of the ECG signal or bioimpedance signal quality. When monitoring for 24 hours, a subject should have 1440 samples per day. Adherence for a specific day is measured as the number of activity samples gathered divided by 1440 (expressed as a percentage). Adherence for a given monitoring period will be the number of days where the daily adherence is greater than 80% divided by the total number of days (expressed as a percentage of days monitored).

**Figure 6** Secondary & Exploratory Outcomes Illustration

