### 3.2 Secondary objectives:

- Quantify the time to the first readmission or death
- Quantify the number of hospital readmissions or ER visits
- Quantify all-cause mortality

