An RN will be designated as the primary coach on the high touch study team focused on disease management including symptom recognition, adherence to treatment strategies, care coordination, medication matters, and problem solving. Medication matters include initial medication reconciliation and the organization of resources to obtain medications for patients who have socioeconomic challenges. A RN will also be responsible for managing socio-economic challenges, and providing a nutrition and wellness assessment and goal setting. The high touch study team establishes a patient-centric relationship using techniques of motivational interviewing coupled with a transactional model of communication. Health literacy will be assessed using a validated tool to help personalize coaching interactions. Coaching topics will include the patient's understanding of their disease, establishing goals of health, treatment strategies, medication adherence, and therapy expectations. As the high touch study team identifies knowledge deficits, they customize the education and employ the teach-back

methodology to address the gaps. The high touch study team will engage the patient in collaborative care planning and goal setting to ensure interventions are congruent with the patient's readiness for change, needs, values, culture, desires, and health goals. Patient engagement and self-care management will be measured with the Self-Care of Heart Failure Index in a pre-test/post-test fashion at the time of enrollment and at 60 days post-enrollment.

The research coordinator will screen patients hospitalized with ADHF. Those who meet all inclusion and exclusion criteria will be randomized with unequal allocation, 4:1 Tele-HC intervention to standard care and enrolled in the study. Demographic and clinical data will be collected.

All patients will be assessed at 30 days and 60 days for the occurrence of re-hospitalization and all-cause mortality. De-identified hospital records will be collected so that the study monitor can review to verify cause of re-hospitalization.

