##### 4.6.2 Secondary Study Endpoints

- Time to readmission or death
- Number of hospital readmissions or ER visits (visits without admissions)

- All-cause mortality

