### **Handling of Missing Data**

Analyses will be conducted under intention to treat principles. All randomized subjects will be analyzed. The primary outcome (all-cause readmission within 60 days of randomization) is expected to be available for all participants through continuity of care documentation, patient/family contacts and medical record searches. Death prior to 60 days will be counted as an event (See Section 7.2.3 below). If there is loss to follow-up in the groups, the cumulative probability of readmission will be estimated using the Kaplan-Meier method as a sensitivity analysis to the primary analysis.

For the remaining outcome variables, all-available-data (for longitudinal measurements) and worst-case imputation will be considered alongside of multiple imputation to test the robustness of study findings to missing data.

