### **7.2.3 Primary Outcomes**

Hypothesis: The 60-day readmission rate will be decreased with the addition of remote monitoring.

To test this hypothesis, a Cochran-Mantel-Haenszel chi-square test of proportions will be used. The stratification factor in this test will be the enrolling clinical site. The primary outcome is all cause readmission, so no adjudication is required for the primary objective. If a participant dies within 60 days of initial hospital discharge prior to any readmission, the participant will be considered as readmitted for the purpose of the primary outcome.

Intention to treat analysis will be used for the primary analysis. If there is loss to follow-up in the groups, the cumulative probability of readmission will be estimated using the Kaplan-Meier method as a sensitivity analysis to the primary analysis. Differences in the hazard rates will be tested using the stratified log-rank test. An additional sensitivity analysis will be conducted using the “per protocol” analysis set (see below), which consists of all subjects that completed the study and were adherent to monitoring.

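### Section 7.2.4 gives a method for time to readmission, not the listed time to readmission or death, and adds an HF-readmission endpoint that is not listed

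*Combined protocol and SAP*

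**What the plan says.** Section 3.2 gives a secondary objective, "Quantify the time to the first readmission or death", and 4.6.2 gives the matching endpoint, "Time to readmission or death". Both include death in the event. The other two listed secondary endpoints are the number of readmissions or ER visits, and all-cause mortality.

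Section 7.2.4 supplies the time-to-event method: "The time to (first) hospital readmission will be modeled using a Kaplan-Meier survival and tested using a stratified log-rank test". It says nothing about death as an event, a censoring reason or a competing event. All-cause mortality has its own stratified log-rank test in the same section.

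Section 7.2.4 also states: "For the secondary endpoint of HF-related readmission, the same analytical approach described for the primary outcome measure will be used". HF-related readmission does not appear in 3.2, in 4.6.2, or among the exploratory outcomes in 4.6.3.

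For the primary outcome, 7.2.3 says that if a participant dies before any readmission, "the participant will be considered as readmitted for the purpose of the primary outcome". The paragraph on missing data repeats this where it discusses the primary outcome: "Death prior to 60 days will be counted as an event (See Section 7.2.3 below".

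**The concern.** A method section should analyse the endpoint that the protocol lists. Here the listed event is readmission or death, and the event in the method is readmission. An analyst working from 4.6.2 would count a death before readmission as an event. An analyst working from the words of 7.2.4 would censor it. They would report different event counts, Kaplan-Meier curves and hazard ratios under one endpoint name.

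HF-related readmission raises two further questions. One is its status, since it is called secondary but is not listed. The other is its event definition. Borrowing the primary's approach could mean only the site-stratified Cochran-Mantel-Haenszel (CMH) test in the intention-to-treat set, or it could also bring the coding of death as a readmission. The text does not say. Secondary outcomes are not adjusted for multiplicity, so a clear list and clear event definitions, fixed before data are seen, are what protect against selective reporting.

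**Working it through.** **Comparison of the text**

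| Outcome | Listed in 3.2 / 4.6.2 | Method in 7.2.4 | Role of death |
|---|---|---|---|
| Time to event | Readmission or death | Kaplan-Meier and stratified log-rank for readmission | Event in the lists, absent from the method |
| HF-related readmission | Not listed | Same approach as the primary | Not stated |
| All-cause mortality | Listed | Stratified log-rank | Event in both |

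The mismatch in the first two rows does not depend on any number.

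**Inputs for an illustration**

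- Readmission by 60 days: 25% in standard care and 12.5% in Tele-HC (section 7.1). I take these as readmission alone, as 7.1 words them. The plan's own figure reproduces from them: a pooled-variance two-proportion calculation at two-sided 0.05 gives 152 per group with 80.0% power. The plan states no figure for the secondary endpoints.
- Total 304. The 4:1 ratio in 4.2 gives 243 and 61; section 7.1 assumes 152 per group.
- Death without readmission, *d*: 2-5%, equal in both arms. This is an assumption. The documents give no rate; section 5.2 excludes a life expectancy under 2 months.
- Constant hazards over 60 days (assumption).

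**Events left out if deaths are censored**

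- Deaths without readmission: 304 × 0.02 = 6.1; 304 × 0.05 = 15.2.
- Readmissions at 4:1: 61 × 0.25 + 243 × 0.125 = 45.6. At 152 per group: 152 × 0.25 + 152 × 0.125 = 57.0.
- Share of composite events lost at 4:1: 6.1/51.7 = 12% to 15.2/60.8 = 25%. At 152 per group: 6.1/63.1 = 10% to 15.2/72.2 = 21%.

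**60-day estimates**

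With readmission probability *p*, the total cumulative hazard is H = −ln(1 − p − d). The readmission part is h = H × p/(p + d). Kaplan-Meier with deaths censored estimates 1 − exp(−h). The composite is p + d.

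| Arm | d | H | h | Deaths censored | Composite |
|---|---|---|---|---|---|
| Standard care | 2% | 0.3147 | 0.2914 | 25.28% | 27.0% |
| Standard care | 5% | 0.3567 | 0.2972 | 25.71% | 30.0% |
| Tele-HC | 2% | 0.1567 | 0.1350 | 12.63% | 14.5% |
| Tele-HC | 5% | 0.1924 | 0.1374 | 12.84% | 17.5% |

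**Contrast between arms**

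- Risk difference, deaths censored: 25.28 − 12.63 = 12.65 points; 25.71 − 12.84 = 12.87 points.
- Risk difference, composite: 27.0 − 14.5 = 12.5 points; 30.0 − 17.5 = 12.5 points.
- Hazard ratio, deaths censored: 0.1350/0.2914 = 0.46; 0.1374/0.2972 = 0.46.
- Hazard ratio, composite: 0.1567/0.3147 = 0.50; 0.1924/0.3567 = 0.54.

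As an estimate of readmission alone, the censored Kaplan-Meier is only 0.1-0.7 points too high. The main problem is therefore that the analysis targets a different quantity from the listed one.

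I give no figure for HF-related readmission. The documents supply neither an expected HF-readmission rate for this trial nor a death rate, so any such figure would combine two unsupported assumptions.

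**The case against.** The strongest reply is that readmission is shorthand. The primary objective (3.1), the general design (4.1), the sample size section (7.1) and the primary hypothesis (7.2.3) all speak of readmission for an endpoint that 4.6.1 defines as readmission or death. On that view 4.6.2 defines the secondary event, 7.2.4 only names the technique, and the death rule in 7.2.3 stays with the primary outcome as worded. This reading is coherent: the composite is analysed, and no death is coded as an HF readmission.

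That much stands. A reader might infer that no consistent interpretation of the plan exists, because the death rule must either be confined to the primary (losing the composite) or be carried over (miscoding HF readmissions). The documents do not support this inference. Nothing requires one rule to govern both endpoints, and 3.2 and 4.6.2 themselves put death in the time-to-event endpoint.

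A reader might also infer that HF-readmission counts would be heavily inflated by deaths. That requires setting aside the explicit limit in 7.2.3, and the more natural meaning of the borrowed approach is the test and the analysis set.

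Two further points are fair. Deaths are not lost to the trial, because mortality is tested separately. And Figure 6, which illustrates the secondary and exploratory outcomes, is not available here and might name the events.

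The shorthand reading has to be supplied by the analyst, however. For the primary outcome, 7.2.3 used an explicit sentence to bring death in; 7.2.4 has no such sentence for the time-to-event endpoint. A statistical plan should not leave an event definition to that choice.

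**Conclusion.** The point holds for secondary endpoints only, and it should be corrected. As written, the time-to-event method does not match the endpoint in 3.2 and 4.6.2; applied literally, it censors deaths before readmission and leaves the listed composite unanalysed. Under the stated assumptions, the arm-level estimates fall by about 2 to 5 points (for example 27.0 − 25.3 = 1.7 and 17.5 − 12.8 = 4.7), and the hazard ratio looks somewhat more favourable to Tele-HC. The risk difference hardly changes, so it would be wrong to infer that the absolute treatment effect is materially distorted. These sizes rest on an assumed, equal death rate and constant hazards; the mismatch of wording does not.

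HF-related readmission is an endpoint of unstated status, and the handling of death in it is unspecified. That is an omission to close, not evidence that deaths will be miscoded.

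The primary analysis, its sample size and the mortality test are not affected. The conclusion rests on the text alone, since Figure 6 could not be consulted; this lowers confidence slightly.

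**What to change.** 1. In 7.2.4, name the time-to-event endpoint as time to first readmission or death, with death counting as an event, and keep Kaplan-Meier and the stratified log-rank test.
2. If readmission alone is also to be reported, use cumulative incidence with death as a competing event.
3. Add HF-related readmission to 3.2 and 4.6.2, or label it exploratory.
4. State that the 7.2.3 coding of death as readmission does not carry over to HF-related readmission, or define that endpoint explicitly as a composite with death. In either case tabulate deaths by arm beside it.
5. Give a working definition of HF-related and name who applies it. Section 7.2.3 waives adjudication only for the primary: "The primary outcome is all cause readmission, so no adjudication is required for the primary objective". A record review already exists under the intervention arm text in 4.3, "De-identified hospital records will be collected so that the study monitor can review to verify cause of re-hospitalization", but 8.4 sends readmission records to the Project Coordinator, so the responsible role should be made clear.

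The cost is a few sentences, the definition, and a little programming. No new data are needed: survival status and hospitalization are already collected at 30 and 60 days, and the cause of re-hospitalization is already checked against records.

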### 7.2.5 Interim Analysis

There is no planned interim analysis for efficacy.

### 7.2.6 Subject Population(s) for Analysis

#### Intention-to-Treat Analysis Set

The primary analysis will be conducted according to modified “Intention-to-Treat” (ITT) principles; that is, each subject will be analyzed according to the randomized treatment arm, whether or not that treatment was actually received and provided they are discharged from the hospital. The ITT method includes analysis of all subjects according to the treatment arm to which they were originally randomized irrespective of protocol violations, crossover, and events arising post randomization. Because randomization carries the expectation of creating treatment arms balanced with respect to known and unknown prognostic factors, removing randomized subjects from the analysis, even for the best of intentions, runs the risk of introducing differential selection biases into the treatment comparisons. Participants not discharged alive or which are transferred to another care facility that prohibits the randomized assignment from being implemented, will be excluded from the ITT analysis set.

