#### 4.5 Study Schema

#### 4.6 Outcome Measures

##### 4.6.1 Primary Study Endpoint

Occurrence of all-cause hospital readmissions or death within 60 days of randomization

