#### Study Withdrawal

If the subject dies after being randomized but prior to hospital dismissal, the subject will be withdrawn from the study.

If the subject is lost to follow up, every effort will be made to contact the subject and determine the reason that will then be documented, including the measures taken to follow-up. If subject withdraws or drops out of the study, the reason for withdrawal from the study is to be documented on the case report form (CRF) and in the source document. The study coordinator or investigator must attempt to document re-hospitalization data unless the subject expressly refuses to provide this information.

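### The plan says that all randomized patients are analysed but also excludes some of them, counts deaths from two different starting points, and has no all-randomized analysis if the exclusion governs

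*Combined protocol and SAP*

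**What the plan says.** **Who is analysed.** The missing-data section states "All randomized subjects will be analyzed". Section 7.2.3 adds, without qualification, "Intention to treat analysis will be used for the primary analysis". Section 7.2.6 calls the primary analysis modified ITT. Patients count by randomized arm "whether or not that treatment was actually received and provided they are discharged from the hospital", and two groups are removed: "Participants not discharged alive or which are transferred to another care facility that prohibits the randomized assignment from being implemented, will be excluded". The same paragraph describes ITT as covering all subjects "irrespective of protocol violations, crossover, and events arising post randomization" and warns that "removing randomized subjects from the analysis, even for the best of intentions, runs the risk of introducing differential selection biases" into the comparison.

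**Which deaths count.** Section 4.6.1 defines the primary endpoint as "Occurrence of all-cause hospital readmissions or death within 60 days of randomization". The missing-data section also treats death before 60 days as an event and describes the outcome as running from randomization. The Study Withdrawal text in section 5.3 says: "If the subject dies after being randomized but prior to hospital dismissal, the subject will be withdrawn from the study". Section 7.2.3 counts a death as a readmission if it falls within 60 days of discharge from the initial stay.

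**What else uses the set.** Section 7.2.4 tests all-cause mortality on the intention-to-treat sample.

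**The concern.** The primary population and the status of some deaths each have two incompatible definitions. If they are not settled in writing, the choice could be made after outcomes are known.

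If section 7.2.6 governs, randomized patients leave both the primary and the mortality analysis because of what happened to them after randomization. That is the risk the section itself describes. The transfer rule needs the closer look, because it turns on whether the assigned arm can be delivered. Tele-HC is standard care plus a device and coaching (section 4.3), so the rule could remove different shares, or different kinds of patient, from the two arms.

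**Working it through.** **Text check**

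| Question | One answer | The other answer |
|---|---|---|
| Are all randomized patients analysed? | Yes: missing-data section; section 7.2.3 unqualified | No: section 7.2.6 |
| Is an in-hospital death after randomization an event? | Yes: section 4.6.1; missing-data section | No: Study Withdrawal; section 7.2.6 |
| When does the 60-day period for deaths start? | Randomization: section 4.6.1 | Discharge: section 7.2.3 |

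The discharge clock fits the withdrawal and exclusion rules, but not section 4.6.1 or the missing-data section.

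The in-hospital death rule reaches only patients randomized before discharge. The schedule in section 6.1 lets randomization run to two working days after dismissal.

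No planned analysis restores the excluded patients. Kaplan-Meier is for loss to follow-up (missing-data section, section 7.2.3). The per-protocol set requires study completion and adherence to monitoring, so it is narrower.

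**Numerical inputs**
- From section 7.1: control rate 25%, a 50% reduction to 12.5%, two-sided alpha 0.05, total 304.
- From section 4.2: 4:1 allocation, so 304 × 4/5 ≈ 243 Tele-HC and 61 standard care.
- Not in the documents, so assumed: the share *t* of Tele-HC patients excluded (1%-10%) and their 60-day event risk *r* (10%-60%).

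**The plan's own figure.** The pooled-variance formula without continuity correction gives n = [1.96·√(2·0.1875·0.8125) + 0.842·√(0.25·0.75 + 0.125·0.875)]² / 0.125² = 152 per group, with power 80.0%. This reproduces section 7.1. That figure assumes equal groups, which is a separate matter, so both splits appear below.

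**Method.** Exact binomial enumeration of the uncorrected, unstratified chi-square test. The planned test is Cochran-Mantel-Haenszel by site, but the number of sites is not given. On this method, power for 25% vs 12.5% is 81% at 152 vs 152 and 66% at 61 vs 243.

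**Bias under no true effect, only Tele-HC patients excluded.** The rate in the remaining Tele-HC patients is (0.25 − t·r)/(1 − t). For example, t = 5% and r = 40% give (0.25 − 0.02)/0.95 = 24.2%, a bias of 0.8 points towards Tele-HC. For 61 vs 243:

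| Excluded | Bias at r = 40%-60% (points) | False finding for Tele-HC, r = 40%-60% | Two-sided error, r = 40%-60% | False finding for Tele-HC, r = 10%-15% |
|---|---|---|---|---|
| none | 0 | 2.8% | 5.0% | 2.8% |
| 1%-2% | 0.2-0.7 | 3.0%-3.7% | 5.1%-5.4% | 2.5%-2.7% |
| 5% | 0.8-1.8 | 3.7%-5.4% | 5.3%-6.4% | 2.0%-2.2% |
| 10% | 1.7-3.9 | 5.0%-10.4% | 6.2%-10.8% | 1.4%-1.8% |

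At 10%-15% risk the bias runs against Tele-HC, by 0.1-1.7 points. The chance of a false finding against it rises from 2.2% to 2.7%-2.9% (5% excluded) or 3.3%-4.0% (10%). At 25% risk nothing material changes (2.7%-2.8% for Tele-HC). Equal exclusion of equal-risk patients from both arms gives no bias. If controls are excluded at half the rate (10% vs 5%), the chance of a false finding for Tele-HC is 3.9%-5.8% at 40%-60% risk.

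At 152 vs 152 the chance of a false finding for Tele-HC is 2.5% with no exclusion. At 40%-60% risk it is 3.5%-5.5% with 5% excluded and 5.1%-11.7% with 10% excluded.

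**In-hospital deaths.** At equal rates in both arms, removing them causes no bias under no effect. Each 1% removes about 3 of 304 patients.

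**The case against.** The strongest reply is that section 7.2.6 is the dedicated definition, says openly that the principle is modified, and would ordinarily govern. Study Withdrawal, section 7.2.3 and section 7.2.6 agree with each other. A patient never discharged cannot be readmitted, and the coaching phases in section 4.4 are counted from discharge. Much of this stands: the in-hospital death part is mainly a conflict over the clock, not a demonstrated bias. It does not dispose of section 4.6.1 or the missing-data section, which say otherwise. The intervention also starts before discharge, since section 4.4 places device application there.

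Three stronger readings are tempting, and the documents do not support them.
- *A reader might infer that the transfer rule favours Tele-HC.* Its wording covers both arms, and section 4.3 ties standard care to staff at the participating institution, so controls could be excluded too. No transfer rate, risk or arm difference is given. A difference by arm is an inference.
- *A reader might infer that the type I error is materially inflated.* In the illustration, two-sided error stays near 5% unless about 5%-10% of Tele-HC patients, no or fewer controls, and mainly high-risk patients are excluded. No section supports that scenario.
- *A reader might take section 8.3, which runs from administration of study treatment, as a third endpoint clock.* It is a reporting period in the safety section.

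It is also fair to say that a prespecified all-randomized sensitivity analysis, with the text reconciled, would remove the contradiction without changing the primary set.

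**Conclusion.** The point holds as a contradiction that must be resolved before analysis. Two statements of the primary population and two rules for deaths cannot both be followed. If section 7.2.6 governs, the excluded patients also leave the mortality test, with no planned analysis to show the comparison with them included. This conclusion rests on the text alone.

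The direction and size of any bias are unknown. The figures above rest on assumed exclusion shares and risks, a 25% rate in both arms and an unstratified test. They show that the effect could be nil, small in either direction, or appreciable if exclusions are frequent, high-risk and concentrated in one arm.

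**What to change.** Reconcile section 4.6.1, Study Withdrawal, the missing-data section, section 7.2.3 and section 7.2.6 to one population and one clock.

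- Make all randomized patients, in their assigned arms, the primary set, as the missing-data section states. Count death after randomization as an event, as section 4.6.1 states, in the primary and mortality analyses.
- Keep the discharged-and-deliverable set, with the discharge clock, as a labelled sensitivity analysis.
- At the least, prespecify the all-randomized analysis of the primary and mortality outcomes as a sensitivity analysis.
- Report exclusions by arm and reason.

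The change is one of wording. No new data collection is expected: Study Completion plans 30- and 60-day survival and hospitalization follow-up for all randomized patients, and the missing-data section expects the outcome for everyone.

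There are two costs. First, index-stay days after randomization use up part of the 60 days. Second, power is diluted. Suppose the overall untreated risk is 25%, Tele-HC halves risk only in patients who can receive it, and a share *t* with risk *r* cannot. The Tele-HC rate is then (0.25 − t·r)/2 + t·r = 0.125 + t·r/2, and power against 25% is:

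| Cannot receive Tele-HC | 61 vs 243, r = 25% / 40% / 60% | 152 vs 152, r = 25% / 40% / 60% |
|---|---|---|
| none | 66% | 81% |
| 1%-2% | 61%-65% across these risks | 76%-80% across these risks |
| 5% | 61% / 58% / 54% | 76% / 73% / 69% |
| 10% | 56% / 50% / 42% | 71% / 64% / 55% |

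The high-risk scenarios that show the most bias also carry the largest power cost.

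Separately, if 1%-2% die in hospital in both arms and count as events, power is about 64%-61% at 61 vs 243, against about 65%-66% with them excluded (79%-76% against about 80% at 152 vs 152).
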